20.1 Variables and derivations

20.1.1 Serious adverse events (SAEs) and treatment-emergent adverse events (TEAEs)

Variables:

- First Study drug administration Date
- Serious AE start Date
- Inform consent date
- Adverse Event Serious i.e. (AESER)

Derivations:

- If Adverse Event Serious i.e. (AESER) = "YES" and Serious AE start Date >= Inform consent date, then we will consider it as serious adverse event (SAE)
- If AE start Date >= First Study drug administration date, then we will consider it as treatment-emergent adverse events (TEAEs)

20.1.2 Rates per 30 days and per subject year of total hypoglycemic events (symptomatic or asymptomatic)

Variables:

- What was the blood glucose level (mg/dL) prior to treating the event? (In eCRF "Hypoglycemia Events" form)
- Were signs/symptoms of hypoglycemia present, other than the blood glucose reading? (In eCRF "Hypoglycemia Events" form)
- Hypoglycemic event start date
- Date of Visit 2 (Week 0)
- Date of Visit 8 (Week 24)
- Date of Visit 9 (Week 28)
- Date of first IMP dose administration (In eCRF "Exposure" form)
- Date of last IMP administration (In eCRF "End of Study" form)

Derivations:

- The symptomatic and asymptomatic i.e. total hypoglycemic events will be identified based on derivation mentioned in section 19.1.1.
- Hypoglycemic event start date ≥ Date of Visit 2 (Week 0) and Hypoglycemic event start date ≤ Date of Visit 8 (Week 24) for accessing the hypoglycemic events from Day 0 to week 24.
- Hypoglycemic event start date ≥ Date of Visit 2 (Week 0) and Hypoglycemic event start date ≤ Date of Visit 9 (Week 28) for accessing the hypoglycemic events from Day 0 to week 28.

The formula used for calculation for rates per 30 days and per subject year (365.25 days) of total hypoglycemic events mentioned below:

The rate of hypoglycemic events per 30 days $= \frac{\text{"The total number of events between the time points"}}{\text{"Actual number of days between the time points"}} * 30$ The rate of hypoglycemic events per year (365.25 days) $= \frac{\text{"The total number of events between the time points"}}{\text{"Actual number of days between the time points"}} * 365.25$ Offset variable for per 30 $= log \left(\frac{\text{"The Duration of treatment exposure"}}{30}\right)$ Offset variable per year $= log \left(\frac{\text{"The Duration of treatment exposure"}}{365.25}\right)$

Note: For the duration of treatment exposure see formula mentioned in section 12.1

20.1.3 Incidence and rates per 30 days and per subject-year of nocturnal, severe, documented symptomatic and asymptomatic hypoglycemic events

Variables:

Page 57 of 85

- What was the blood glucose level (mg/dL) prior to treating the event? (In eCRF "Hypoglycemia Events" form).
- Were signs/symptoms of hypoglycemia present, other than the blood glucose reading? (In eCRF "Hypoglycemia Events" form).
- When did the hypoglycemic event occur? (In eCRF "Hypoglycemia Events" form).
- Did the subject experience a severe hypoglycemic episode with neurological (cognitive) impairment requiring assistance from another person? (In eCRF "Hypoglycemia Events" form).
- Hypoglycemic event start date
- Date of Visit 2 (Week 0)
- Date of Visit 8 (Week 24)
- Date of Visit 9 (Week 28)
- Date of first IMP dose administration (In eCRF "Exposure" form)
 Date of last IMP administration (In eCRF "End of Study" form)

Derivation:

- Hypoglycemic event start date ≥ Date of Visit 2 (Week 0) and Hypoglycemic event start date ≤ Date of Visit 8 (Week 24) for accessing hypoglycemic events from Day 0 to week 24 (for the incidence and rate of hypoglycemic events endpoint).
- Hypoglycemic event start date ≥ Date of Visit 2 (Week 0) and Hypoglycemic event start date ≤ Date of Visit 9 (Week 28) for accessing hypoglycemic events from Day 0 to week 28 (only for the rate of hypoglycemic events endpoints).
- If in eCRF "Hypoglycemia Events" form the question if, the question "What was the blood glucose level (mg/dL) prior to treating the event hypoglycaemic event occur" result is less or equal to 54 mg/dL and the question "when did the hypoglycemic event occur" is answered as "BETWEEN BEDTIME AND PRIOR TO FIRST MEAL IN MORNING" then we will consider it as nocturnal hypoglycemia.
- If in eCRF "Hypoglycemia Events" form the question "What was the blood glucose level (mg/dL) prior to treating the event hypoglycaemic event occur" result is less or equal to 54 mg/dL and the question "Did the subject experience

a severe hypoglycemic episode with neurological (cognitive) impairment requiring assistance from another person" is answered as "YES" then we will consider this as severe hypoglycemia.

• For Documented symptomatic hypoglycemia and documented asymptomatic hypoglycemia see the derivation mentioned in section 19.1.1.

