### 9.1. Efficacy and Safety Assessments

#### 9.1.1. Primary Safety Assessments

##### Hypoglycemia

Information on treatment-emergent hypoglycemic events starting from Visit 2 until the last study visit (Visit 9 or early termination [ET] visit) will be collected. Subjects will be trained about signs and symptoms of hypoglycemia. Subjects will be trained to check and record their blood glucose levels if they experience symptoms suggestive of hypoglycemia. For each hypoglycemic event, subjects should record the following data in the study diaries provided by the sponsor via the investigator:

- blood glucose levels
- associated symptoms
- treatment, and
- other pertinent information.

A hypoglycemic event is defined as any time a subject feels that he or she is experiencing a sign or symptom that is associated with hypoglycemia or has a FBG level of  $\leq 54$  mg/dL (3.0 mmol/L), even if it was not associated with signs, symptoms, or treatment consistent with current guidelines.

**Severe hypoglycemia:** An event requiring assistance of another person to actively administer carbohydrates or glucagon or taking other corrective actions. Blood glucose concentrations may not be available during an event, but neurologic recovery following the return of blood glucose to normal levels is considered sufficient evidence that the event was induced by a low blood glucose concentration.

**Nocturnal hypoglycemia:** Any total hypoglycemic event that occurs after bedtime and prior to the first meal in the morning.

**Documented symptomatic hypoglycemia:** An event during which typical symptoms of hypoglycemia are accompanied by a blood glucose level of  $\leq 54$  mg/dL ( $\leq 3.0$  mmol/L) as confirmed by blood glucose measurement.

**Asymptomatic hypoglycemia:** Any event not accompanied by typical symptoms of hypoglycemia but a measured a blood glucose level of  $\leq 54$  mg/dL ( $\leq 3.0$  mmol/L) was observed.

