### 10.3. Statistical Analyses

#### 10.3.1. General Statistical Considerations

All data will be entered, verified, and archived by a contract research organization (CRO) external to Lilly and/or at Lilly. Data listings, summaries, and analyses will be performed by a CRO under the guidance and approval of statisticians at Lilly. Statistical analysis of this study will be the responsibility of Lilly.

Any change to the data-analysis methods described in the protocol will require an amendment ONLY if it changes a principal feature of the protocol. Any other change to the data analysis methods described in the protocol, and the justification for making the change, will be described in the statistical analysis plan and/or in the clinical study report. Additional exploratory analyses will be conducted as deemed appropriate.

Safety and efficacy analyses will be conducted on the full analysis set (FAS) or safety set. These sets include all data from all enrolled subjects who take at least 1 dose of study treatment.

All tests of treatment effects will be conducted at a 2-sided alpha level of 0.05, unless otherwise stated.

The planned statistical method for the primary analysis is the calculation of the estimate and the 95% confidence interval for the incidence of total (symptomatic or asymptomatic with FBG level  $\leq 54$  mg/dL [3.0 mmol/L]) hypoglycemic events at Week 24.

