### **10.3.2. Safety Analyses**

#### **10.3.2.1. Hypoglycemic Events**

The primary endpoint of this study is the incidence of total (symptomatic or asymptomatic with FBG level  $\leq 54$  mg/dL [3.0 mmol/L]) hypoglycemic events at Week 24. The events will be analyzed as following as number and percentage of subjects experiencing at least 1 event over the study period. A 95% confidence interval for the rate will be calculated using the normality assumption.

The rate of total (symptomatic or asymptomatic with FBG level  $\leq 54$  mg/dL [3.0 mmol/L]) hypoglycemic events will be analyzed as follows:

- Number of hypoglycemic events per subject over the study period will be analyzed as continuous variables as per Section 10.3.1 (mean, median, SD, standard error [SE], minimum, and maximum)
- The rate of hypoglycemic events per 30 days, and the rate per year, that is the number of hypoglycemic events per subject year (365.25 days), will be calculated.
  - The rate per 30 days between 2 time points (end of treatment/study vs. baseline) is defined as the total number of events between the time points divided by the actual number of days between the time points, and then multiplied by 30. A similar approach is then used for the number of events per subject-year (365.25 days).
  - These measures will be summarized for the overall study period and will be assessed using a negative binomial model with baseline HbA1c as covariate and the log of the study treatment exposure time as offset variable.

The following types of hypoglycemia (see Section 9.1.1) will be analyzed similarly (incidence and rates) as specified for total hypoglycemia:

- nocturnal hypoglycemia
- severe hypoglycemia
- documented symptomatic hypoglycemia, and
- asymptomatic hypoglycemia

All analyses for the hypoglycemic events will be repeated for the PPS population.

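### SAP 20.1.3 counts an assisted episode as severe hypoglycemia only with a reading of 54 mg/dL or below, a condition the protocol does not set, so severe incidence and crude rates can only be understated or unchanged

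*SAP*

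**What the plan says.** Protocol 9.1.1 defines severe hypoglycemia as "An event requiring assistance of another person to actively administer carbohydrates or glucagon or taking other corrective actions". The definition contains no glucose value. It goes on to say that "Blood glucose concentrations may not be available during an event" and that "neurologic recovery following the return of blood glucose to normal levels is considered sufficient evidence" of a low-glucose cause. Protocol 10.3.2.1 ties the analysis to that definition: "The following types of hypoglycemia (see Section 9.1.1) will be analyzed similarly (incidence and rates) as specified for total hypoglycemia", with severe hypoglycemia on the list that follows.

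SAP 20.1.3 derives the category differently. The eCRF glucose value before treatment "result is less or equal to 54 mg/dL and the question 'Did the subject experience" the assisted episode must be answered YES; "then we will consider this as severe hypoglycemia". The eCRF question, as the SAP reproduces it, asks about "a severe hypoglycemic episode with neurological (cognitive) impairment requiring assistance from another person".

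SAP 20.2.3 uses this derivation for the severe incidence and rate outputs. SAP 8.2 lists the variables to be imputed. Glucose at a hypoglycemic event is not among them, and all other missing data are left missing.

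**The concern.** The SAP adds a second condition that the protocol does not have. The condition removes the situation the protocol foresaw: someone else had to intervene and no reading was taken. Severe hypoglycemia is a named secondary safety endpoint in a study whose primary objective is the risk of hypoglycemia, and the added condition can move the result in one direction only, towards less apparent harm.

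Protocol 10.3.1 allows analysis methods to change without an amendment when no principal feature is affected, but the change "and the justification for making the change, will be described in the statistical analysis plan and/or in the clinical study report". SAP 20.1.3 neither presents this as a change nor gives a reason for it.

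Protocol 9.2.1 also makes severe hypoglycemia an SAE criterion. The same assisted episode could thus be an SAE of severe hypoglycemia and yet be missing from the severe hypoglycemia table.

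**Working it through.** **No planned figure to reproduce.** The documents give no expected number, rate or precision for severe hypoglycemia, and no share of assisted episodes without a reading at or below 54 mg/dL. The check is therefore a comparison of rules, followed by an illustration.

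**Which events each rule counts** (assistance question answered YES):

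| Glucose before treatment | Protocol 9.1.1 | SAP 20.1.3 as written |
|---|---|---|
| ≤54 mg/dL | severe | severe |
| Not available | severe (expressly provided for) | not shown to meet ≤54, so not severe |
| >54 mg/dL | severe (follows from the absence of a threshold) | not severe |

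**Is a threshold implied elsewhere?** No. Protocol 9.1.1 builds the total-event concept into the nocturnal definition and the 54 mg/dL limit into the documented symptomatic and asymptomatic definitions. It puts neither into the severe definition.

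**Direction.** The SAP's severe events are a subset of the events answered YES. Incidence is divided by the analysis population (SAP section 9) and the crude rate by days between time points (SAP 20.1.2). Neither denominator depends on how an event is classified, so both measures can only fall or stay equal. In 5,000 simulated trials there was no exception for incidence, the pooled crude rate or the mean per-subject rate, whether or not a missing reading was treated as satisfying the limit.

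**Missing readings in the program.** The analysis is in SAS (SAP 7.6). A plain test of ≤54 in SAS treats a missing numeric value as low and would admit the episode; a test that first requires a non-missing value would exclude it. The SAP does not say which applies. Readings above 54 are excluded either way.

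**Illustration.** Assumed: 250 subjects treated (the enrolment target in protocol 10.1), 4 of them with one severe event each by the protocol definition. Clopper-Pearson 95% limits for k of n are the 2.5% point of Beta(k, n−k+1) and the 97.5% point of Beta(k+1, n−k); the lower limit is 0 when k = 0.

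| Case | Counted as severe | Incidence (95% CI) |
|---|---|---|
| All four have a reading ≤54 | 4/250 | 1.6% (0.44–4.05%) |
| One without a reading, one >54; missing value admitted by the code | 3/250 | 1.2% (0.25–3.47%) |
| Same, rule as written | 2/250 | 0.8% (0.10–2.86%) |
| None has a reading ≤54; missing readings fail the test | 0/250 | 0% (0–1.46%) |

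**Pooled crude rates to Week 24.** Exposure lies between 200 × 168 / 365.25 = 92.0 subject-years (the planned 20% drop-outs contribute nothing) and 250 × 168 / 365.25 = 115.0 (everyone completes).

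- 4 events: 4/115.0 to 4/92.0 = 0.035 to 0.043 per subject-year
- 3 events: 0.026 to 0.033
- 2 events: 0.017 to 0.022
- 0 events: 0

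To Week 28, which SAP 20.1.3 also requires for rates, the same formula with 196 days gives 107.3 to 134.2 subject-years, and 0.030 to 0.037 for 4 events. With exposure unchanged, the pooled SAP rate equals the protocol rate times the share of assisted events with a reading ≤54.

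**Model-based rate.** The subset argument does not carry over strictly to the negative binomial estimate at mean baseline HbA1c. This was checked with 4 events in 250 subjects, HbA1c assumed uniform from 7 to 11%, equal follow-up, a log-rate slope of 0 or −0.5 per HbA1c point, and a Poisson fit as the limit without overdispersion. Dropping one or two events raised the estimate in between 0.4% and 7.6% of simulated data sets. The model estimate will usually, but not always, move down too.

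**The case against.** The strongest reply is that little hangs on this. Severe hypoglycemia is one of many secondary endpoints in a single-arm study with no comparison test and no decision rule. The effect may be zero. SAEs are tabulated and listed (SAP 16.2.3 and 16.2.9), and every hypoglycemic event is listed (SAP 19.2.1). All of that is true: the signal survives. It does not make the endpoint table correct.

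Second, protocol 10.3.1 lets the justification appear in the study report instead of the SAP, and SAP section 5 defers deviations to that report. Silence in the SAP is therefore not in itself a breach. But a later explanation would not correct the rule, and nothing shows the departure was intended.

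Third, the case for readings above 54 mg/dL is weaker than the case for missing ones, because protocol 9.1.1 says nothing specific about them. This stands as a difference in strength. Their inclusion rests only on the absence of a threshold.

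Fourth, deleting the limit does not fully restore the protocol definition. The eCRF question requires neurological impairment, which protocol 9.1.1 does not. SAP 19.1.1 also requires ≤54 mg/dL for total events, so an episode could then be severe without being a total event. Both points stand and need reconciling; neither supports keeping the limit in the severe rule.

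Finally, the severe and SAE tables can differ legitimately, because SAEs run from consent to the last visit while severe incidence stops at Visit 8. That is so, but differences caused by the glucose condition would come on top of it.

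**Conclusion.** The concern holds. SAP 20.1.3 contradicts protocol 9.1.1 on what counts as severe hypoglycemia, and the direction for incidence and crude rates is certain: understated or unchanged, never overstated. The size is unknown and may be zero. It depends on how many assisted episodes occur and how many have no reading at or below 54 mg/dL, and the documents give neither. Severe events are likely to be few, so single exclusions matter: under the assumed 4 of 250, losing two halves the estimate. This should be corrected before the analysis, because it concerns a named safety endpoint and the error can only favour the product.

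**What to change.** In SAP 20.1.3, delete the 54 mg/dL condition from the severe derivation, so that an event is severe when the severe-episode question is answered YES, whatever the reading. State explicitly that events with a missing reading and events with a reading above 54 mg/dL are counted, so that the result does not depend on how SAS handles a missing value. If a glucose-confirmed severe count is also wanted, present it as a separate labelled line with its justification.

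Alongside this, reconcile the impairment wording of the eCRF question with protocol 9.1.1 and 7.8.3, say how severe events without a qualifying reading relate to the total-event derivation in SAP 19.1.1, and compare the severe table with the SAE records before database lock.

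The main change costs one condition in the SAP text and in the program. It moves the SAP back towards the protocol, so no protocol amendment is needed. The price is that reported severe incidence and crude rates may be somewhat higher. Comparison with the SAE records is a data-review step. The eCRF wording may not be resolvable in the SAP alone.

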20.1.4 Change in HbA1c levels at Weeks 12 and 24 from baseline

Variables:

- HbA1c Results (we will get this data from laboratory in results forms)
- Start date of concomitant medication (From eCRF form: "Concomitant Therapy: Special Interest Hyperglycaemia (For rescue medication)")
- Date of first dose administration
- Date of collection of HbA1c at week 24

Derivations:

- Change in HbA1c = Post visit Baseline visit
- If start date of concomitant medication (Special form) > Date of first dose administration, then this HbA1c result data will not be considered for analysis and we will consider this value as missing.
- If week 24 (HbA1C results) = missing or start date of concomitant medication (Special form) < Date of collection of HbA1c at week 24, then we will use LOCF i.e. previous visit value we will carry forward to visit (week 24).

20.1.5 Percentage of subjects reaching HbA1c targets ≤6.5% and <7% at week 24

Variables:

 HbA1c Results at week 24 (we will get this data from laboratory in results forms)

Derivations: Criteria for identifying the subjects reaching target level is mentioned below for both cases,

- HbA1c level ≤ 6.5%
- HbA1c level ≤ 7%

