## **7.4. Dosage Modification**

The doses may be titrated by 2 to 4 units once or twice in a week until FBG levels are lowered to <100 mg/dL (5.6 mmol/L) as tabulated in [Table ABEX.4](#).

Investigators will be trained to assess when they need to intervene the treatment regimen of subjects who do not reach glycemic targets. If any of the FBG values for 2 consecutive weeks exceed the limits outlined below with no other possible cause of hyperglycemia, rescue medication (more OAMs or GLP-1 RA or bolus insulin; switching to a different basal insulin is not permitted as decided by the investigator) will be prescribed in addition to the ongoing treatment.

- FBG >270 mg/dL (>15.0 mmol/L) from baseline to Week 6 (4 values/week)
- FBG >240 mg/dL (>13.3 mmol/L) from Week 6 to Week 12 (4 values/week)
- FBG >200 mg/dL (>11.1 mmol/L) from Week 12 to end of trial (4 values/week)
- HbA1c  $\geq 8.5\%$  ( $\geq 69.4$  mmol/mol) by and after Week 24

The dose and name of rescue medication must be properly documented in the eCRF. Subjects who had to use rescue medication during the study period will be excluded from the per protocol set (PPS) population.

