#### 10.3.3. Efficacy Analyses

##### 10.3.3.1. Actual and Change from Baseline HbA1c

The actual and change in HbA1c level from baseline to Week 12 and Week 24 will be analyzed using descriptive statistics (mean, median, SD, SE, minimum, maximum, and number with missing values). For subjects requiring rescue medication (see Section 7.4), HbA1c values recorded after the first administration of rescue medication will not be considered for analysis, and these values will be considered as missing. In addition, for the actual value and change from baseline, a descriptive analysis using LOCF will be performed, using the baseline or 12-week value, if the 24-week value is missing or occurred after use of rescue medication.

Additionally, the change in HbA1c level from baseline to Week 24 will be analyzed using the general linear model for the FAS population. The general linear model will evaluate the change from baseline in HbA1c level as the dependent variable and the baseline value of HbA1c as covariate.

All the HbA1c analyses described will be repeated for the PPS population.

##### 10.3.3.2. Subjects Reaching HbA1c Targets ( $\leq 6.5\%$ or $< 7\%$ ) at Week 24

Subjects reaching HbA1c levels of  $\leq 6.5\%$  and  $< 7\%$  at Week 24 will be analyzed descriptively as binary variable, using number and percentage. The HbA1c values used to calculate this binary variable will be the LOCF value, that is, in case the Week 24 value is missing, the Week 12 value will be used. The denominator will be the total FAS population. Subject with missing HbA1c data at Week 12 and Week 24 will be considered as not having reached the target.

These analyses will be repeated for the PPS population.

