8.2 Missing data

- Vital Signs: we will use the last observation carry forward (LOCF) method for the missing values.
- 2) Actual and Change from Baseline HbA1c: For subjects requiring rescue medication, HbA1c values recorded after the first administration of rescue medication will not be considered for analysis, and these values will be considered as missing. In addition, for the actual value and change from baseline, a descriptive analysis using LOCF will be performed, using the baseline or 12-week value, if the 24-week value is missing or occurred after use of rescue medication.
- 3) Subjects Reaching HbA1c Targets (≤6.5% and <7%) at Week 24: The HbA1c values used to calculate this binary variable will be the LOCF value, that is, in case the Week 24 value is missing, the Week 12 value will be used. The denominator will be the total FAS population. Subject with missing HbA1c data at Week 12 and Week 24 will be considered as not having reached the target.

For other efficacy parameters 7-point SMBG levels (mg/dL and mmol/L), body mass index (kg/m²), body weight (kg), basal insulin dose (U/day and U/kg/day) we will apply the LOCF method for missing data.

4) ITSQ score: If an item score is missing for a subject and ≤20% of the items within the domain (or overall) are missing for that subject, then the mean of the items scores in the domain (or overall) will be imputed for the missing item score(s). If there are >20% missing items, the individual subject domain (or overall) score will be set to missing. that is here we will use the mean imputation method.

Page 25 of 85

Change at Week 24 from Week 4 for ITSQ score (Transformed overall and domain scores): we will use the last observation carry forward (LOCF) method for the missing values.

5) Laboratory data: we will use the last observation carry forward (LOCF) method for the missing values.

For all other cases the missing data will not be imputed for this trial.

9. Output presentations

This is single arm study; we are not doing any stratification we will present the summary table for single treatment group i.e. Basaglar.

The Section 23, Appendix 1 describe the format and content for presentation of tables, listings and figures (TLFs).

All percentages (%) for a specific summary are calculated using the total number of participants included in the relevant analysis population as the denominator, unless otherwise specified.

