15.1 Variables and derivations

In eCRF "Concomitant Medications: General Use" form we are capturing the concomitant medication related data.

Concomitant medications are defined as any medication taken after first administration of the IMP till the end of the trial.

All medications will be coded using the WHO-DD, dated (refer to DMP for dictionary date) All concomitant therapies that was originally mapped using the WHO Drug Dictionary in the ClinTrial database will be further classified using Anatomical Therapeutic Chemical (ATC) codes for reporting purposes.

The following parameters will be summarised separately for the subject's with concomitant medication and Special Interest Hyperglycaemia related concomitant medication:

- Number of subjects with at least one concomitant medication and Special Interest Hyperglycaemia related concomitant medication
- Number of subjects for each concomitant medication and Special Interest Hyperglycaemia related concomitant medication by ATC and PT.

The following variables will be listed concomitant and other medications:

- Subject Number
- Medication class/ Standardized medication name/ Reported term
- Dose and unit
- Frequency
- Route
- Start date of medication
- End date of medication

Rescue Medication:

The rescue medication related data will be captured in "Concomitant Therapy: Special Interest Hyperglycaemia" special form in eCRF.

The rescue medication we will identify using following variables:

- Date of first dose administration
- First Rescue medication date

Derivations:

All concomitant medication and Special Interest Hyperglycaemia related concomitant medication, which are identifies as follows:

 If start date of concomitant medication >= Date of first dose administration, then we will consider it as "concomitant medication".

For identification of rescue medication visit wise we will use the following derivation:

(First Rescue Medication Date – Date of First Dose Administration) +1

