20.2.4 Change in HbA1c levels at Weeks 12 and 24 from baseline

| Population: | FAS and PPS |
|-----------------|-----------------|
| Stratification: | Table: By visit |

Listing: by subject

Statistics: The actual and change from baseline data of HbA1c levels will be summarised as (n, mean, standard deviation, standard error, median, minimum, maximum and number with missing values).

The change from baseline variable and the missing HbA1c results imputation i.e. LOCF will be done by using derivations mentioned in section 20.1.4 and the efficacy tables will be presented for with and without imputed values separately for each population set.

The change in HbA1c level from baseline to Week 12 and baseline to week 24 will be analysed using the general linear model.

The change from baseline in HbA1c level as dependent variable and the baseline value of HbA1c as covariate.

The estimate, 95% confidence interval and p-value will be summarised for efficacy table.

The regression line for the general linear model without categorical variable is as follows:

 $Y = \alpha + \beta (X)$

Where,

Y= The response change in HbA1c levels.

 $\alpha = Intercept$

 β =slope

X= Covariate i.e. Baseline HbA1c results

The hypothesis is as follows

H0: $\beta = 0$

i.e. There is no statistically significant change in HbA1c levels at week 12 and 24 from baseline depending on the baseline HbA1c.

V/s

H1: β ≠ 0

i.e. There is statistically significant change in HbA1c levels at week 12 and 24 from baseline depending on the baseline HbA1c.

The above hypothesis will be tested based on α (alpha)=0.05, if the p-value ≥ 0.05 then we will conclude that there is no statistically significant change in HbA1c levels at week 12 and 24 from baseline i.e. Ho is accepted.

The sample SAS programme is as follows:

proc mixed data=dataset;

model Y= X / s cl;

estimate "Model with Mean baseline HbA1C" int 1 HbA1c_baseline mean /CL;

ods output estimates=output dataset;

run; quit;

The listing of the HbA1c data will be provided containing the additional variable for identification of the HbA1C results measured after intake of rescue medication.

20.2.5 Percentage of subjects reaching HbA1c targets ≤6.5% and <7% at week 24

| Population: | FAS and PPS | |
|-----------------|--|--|
| Stratification: | Table: NA | |
| | Listing: NA | |
| Statistics: | Subjects reaching HbA1c levels of ≤6.5% and <7% at Week 24 will be identified as derivation mentioned in section 20.1.5. | |
| | | |

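### SAP 20.1.4 ties the HbA1c rescue exclusion to the first-dose date instead of the sample date, and SAP 20.1.5 codes the <7% target as ≤7%

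*SAP*

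**What the plan says.** **Rescue rule.** Protocol 10.3.3.1 states that "HbA1c values recorded after the first administration of rescue medication will not be considered for analysis" and treats them as missing. SAP 8.2 point 2 repeats this and defines the carry-forward as "using the baseline or 12-week value, if the 24-week value is missing or occurred after use of rescue medication".

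SAP 20.1.4 turns this into derivations. Its second bullet reads "If start date of concomitant medication (Special form) > Date of first dose administration, then this HbA1c result data will not be considered", and the value is then treated as missing. Its third bullet covers a Week 24 result that is missing or drawn after rescue began: "then we will use LOCF i.e. previous visit value we will carry forward to visit (week 24". The only HbA1c date in the variable list is "Date of collection of HbA1c at week 24"; there is no Week 12 collection date. SAP 20.2.4 makes the section operative: "the missing HbA1c results imputation i.e. LOCF will be done by using derivations mentioned in section 20.1.4".

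**Target.** SAP 3.2, SAP 8.2 point 3, the heading of SAP 20.1.5, SAP 20.2.5 and Protocol 10.3.3.2 all give the second target as strictly below 7%. The derivation line in SAP 20.1.5 uses ≤7%, and SAP 20.2.5 identifies responders by that derivation.

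**The concern.** The second bullet of SAP 20.1.4 never asks when the HbA1c sample was taken. It asks only whether rescue began after first dose, which holds for essentially every rescued subject. Results drawn before rescue, which the protocol keeps, are therefore lost. Rescue follows poor control, so the deletion depends on the outcome being summarised.

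The loss can reach a Week 24 result that itself led to rescue. Protocol 7.4 sets an HbA1c rescue limit "by and after Week 24", and SAP 15.1 takes in later medication: "Concomitant medications are defined as any medication taken after first administration of the IMP till the end of the trial".

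The bullets also conflict. The third assumes that an earlier value survives, and the second has removed it. Two competent programmers could produce different tables.

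The ≤7% code counts a result of exactly 7.0% as reaching target, so the reported percentage would not be the stated endpoint.

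**Working it through.** The plan gives no figure of its own to reproduce here. The check compares the rules and then sizes the effect under stated assumptions.

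**1. The two rescue rules on example subjects.** SAP Table 7.1 places Week 12 at Day 84 and Week 24 at Day 168.

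| Rescue starts | Protocol 10.3.3.1 and SAP 8.2 | SAP 20.1.4, second bullet, read literally |
|---|---|---|
| Day 50 | Baseline kept; Weeks 12 and 24 missing | Weeks 12 and 24 missing; baseline too if the wording covers it |
| Day 100 | Baseline and Week 12 kept; Week 24 missing | Week 12 also missing; baseline too if covered |
| Day 175 | All kept | Weeks 12 and 24 missing; baseline too if covered |

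For Day 100, the third bullet would carry forward the Week 12 value that the second bullet has removed. For Day 50, the third bullet used alone carries a post-rescue Week 12 value to Week 24, contrary to SAP 8.2.

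**2. Week 12 change, non-imputed.** Let f be the fraction of subjects with a Week 12 value who are rescued later, and d the amount by which their Week 12 change is worse than that of the others. The full mean is A + f·d. Deleting those subjects leaves A, so the shift is f·d. The documents give neither input.
- d = 0.8: 0.8 × 0.02 = 0.016; 0.8 × 0.05 = 0.04; 0.8 × 0.10 = 0.08.
- Range: 0.4 × 0.02 = 0.008 to 1.2 × 0.10 = 0.12.

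**3. Week 24 change, non-imputed, rescue started after the Week 24 sample.** Assume Week 24 HbA1c is normal with mean 7.5 and SD 1.0, and that a share s of subjects at or above 8.5 lose their value. With z = (8.5 − 7.5)/1.0 = 1, tail probability p = 0.159 and normal density φ(1) = 0.242, the shift is −s·SD·φ(z)/(1 − s·p).
- s = 10%: −0.0242/0.984 = −0.025.
- s = 25%: −0.0605/0.960 = −0.063.
- s = 50%: −0.121/0.921 = −0.131.
- Over means 7.2–8.0 and SDs 0.8–1.2, the same shares give −0.009 to −0.264.

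**4. Week 24 change with LOCF.** If the Week 12 value is blanked and baseline is carried forward, the subject's change becomes 0. With fraction f rescued after Week 12 and Week 12 change c in those subjects, the mean moves toward zero by f·|c|. For f of 5–20% and c of −0.5 to −1.0, this is 0.05 × 0.5 = 0.025 to 0.20 × 1.0 = 0.20 points. If baseline is blanked too, nothing is left to carry forward.

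**5. Target.** With reporting to 0.1%, the probability of a recorded 7.0 is P(6.95 ≤ X < 7.05).

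| Assumed mean, SD | At 7.0 | Of 200 evaluable | Points on FAS of 250 (× 200/250) |
|---|---|---|---|
| 7.2, 0.8 | 4.83% | 9.7 | 3.86 |
| 7.5, 1.0 | 3.52% | 7.0 | 2.82 |
| 8.0, 0.8 | 2.28% | 4.6 | 1.83 |

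The last column assumes that the 50 non-completers have no usable value. With reporting to 0.01%, P(6.995 ≤ X < 7.005) is 0.48%, 0.35% and 0.23%, or 1.0, 0.7 and 0.5 of 200 subjects.

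**The case against.** The strongest reply is that the SAP states the right rule elsewhere. SAP 8.2 point 2 follows the protocol, and SAP 20.2.4 asks for a listing flag on HbA1c results measured after rescue, which requires the measurement date. SAP 15.1 uses the first-dose date to recognise on-study medication, so the second bullet may be that identifier with the collection-date clause left out. A programmer who reads SAP 8.2 could get it right. This shows what was intended, but SAP 20.2.4 sends the programmer to 20.1.4, and the same condition recurs for FBG in 20.1.6 and SMBG in 20.1.8. The contradiction stands.

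The direction of bias is not uniform. Non-imputed changes look better, while LOCF that falls back to baseline looks worse. That is correct, and it limits any directional claim to the particular table and reading.

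The Week 24 case needs rescue to be recorded after the Week 24 sample. SAP 15.2 tabulates rescue only up to Week 24, and Protocol 7.8.2 covers treatment after completion. The case is possible under Protocol 7.4, but its frequency is unknown.

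The ≤7% may be a one-character slip, and a misread symbol cannot be fully excluded. The heading of the same section shows <7%, and the symbol should be checked in the signed SAP. Finally, these are secondary endpoints in a single-arm trial. That bears on severity and not on whether the lines are wrong.

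**Conclusion.** Both derivations are wrong as written, and each contradicts other parts of the SAP as well as the protocol. Confidence in the textual mismatch is high. The numerical effects are scenarios that rest on assumed rescue rates, HbA1c distributions and reporting precision.

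Under those assumptions the rescue rule shifts mean HbA1c changes by roughly a hundredth to a quarter of a percentage point. The sign depends on whether the table is imputed. The target error adds about 2–4 points to the responder rate with 0.1% reporting and is negligible with 0.01%. The primary hypoglycemia analysis and the sample size are untouched. The SAP should be corrected before programming is finalised.

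**What to change.** - **SAP 20.1.4:** set an HbA1c value to missing only if its own collection date is after the first rescue date, at Weeks 12 and 24 alike. Add the Week 12 collection date to the variables. Define LOCF as the last pre-rescue value (Week 12, otherwise baseline), in line with SAP 8.2 point 2.
- **SAP 20.1.5:** change ≤7% to <7%. State whether a post-rescue value can count toward the target: SAP 8.2 point 3 does not say, and whether point 2 extends to it is open to argument.
- **SAP 20.1.6 and 20.1.8:** anchor the same condition to the FBG or SMBG collection date. The protocol states a rescue exclusion for HbA1c only, so the SAP should say that the FBG and SMBG exclusion is its own addition.

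The cost is a few derivation lines, one date variable and one inequality. No new data collection is expected, since the rescue start date and the Week 24 collection date are already listed. The reported responder rate may be slightly lower.
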